4.8.3 DISPENSING LENS PAIR #1

The participant will be assigned a randomization ID and the first pair (lens pair #1) of contact lenses (either test or control lens) will be selected according to the randomization table.

[figure not shown]
Lens pair #1 will be provided to participants in a manner which does not unmask the participant or investigator, as described in Section 4.7.4.

The lenses will be inserted by the participant.

The contact lenses will be allowed to settle for 10 minutes.

The participant will be asked to give subjective ____ratings (Appendix 9) for:

[figure not shown]
- a) Comfort at insertion (0-10 scale)
- c)
- d) Ease of insertion (0-10 scale)
- a) Lace of incertion (e to ocale)

4.8.4 1-MONTH FOLLOW-UP OF PAIR #1

Participants will be asked to wear lenses for at least 4 hours prior to the visit appointment. Participants who attend without lenses in-situ (wearing lenses) for at least four hours will be rescheduled (unless they report problems when wearing the lenses).

	articipant will be asked to score their subjective responses by reflecting on a typi
day di	uring the previous week of lens wear, includes the following:
0	
0	Overall comfort (0-10 scale)
0	Overall dryness (0-10 scale)
0	Ease of insertion (0-10 scale)
0	Ease of removal (0-10 scale)

The lenses will be removed. Lens disposal procedures are detailed in Section 4.7.6.

4.8.5 DISPENSING LENS PAIR #2

The participant will be assigned the second pair (lens pair #2) of contact lenses (either test or control lens) will be selected according to the randomization table.

Lens pair #2 will be provided to participants in a manner which does not unmask the participant or investigator, as described in Section 4.7.4.

[figure not shown]
The lenses will be inserted by the participant.

The contact lenses will be allowed to settle for 10 minutes.

The participant will be asked to give subjective ___ratings (Appendix 9) for:

- g) Comfort at insertion (0-10 scale)
- j) Ease of insertion (0-10 scale)

EX-MKTG-91 PIANO-2 Protocol_14feb2018.docx

- Participant will be provided with more contact lens care solution, new lens case, and lens care verbal re-instruction.
- The participant will be reminded to bring back the remaining lens care solution and lens case to the next visit, 1-month visit of lens pair #2.

4.8.6 1-MONTH FOLLOW-UP OF PAIR #2 & STUDY EXIT

Participants will be asked to wear lenses for at least 4 hours prior to the visit appointment. Participants who attend without lenses in-situ (wearing lenses) for at least four hours will be rescheduled (unless they report problems when wearing the lenses).

·
The participant will be asked to score their subjective responses and indicate any
preference between the two lens types by reflecting on a typical day during the previous
week of lens wear, as detailed in the subjective ratings form
the following:
 Overall comfort (0-10 scale)
 Overall dryness (0-10 scale)
■ Ease of insertion (0-10 scale)
■ Ease of removal (0-10 scale)

The lenses will be removed. The disposal procedures are detailed in Section 4.7.6.

The study exit form will be completed when a participant exits the study. This form will be completed either at study completion, or if the participant is discontinued from the study at another time. A study exit form must be completed for all participants who have taken a study ID number. If in the opinion of the investigator post-study follow-up visits are required, the exit form will be completed after the last follow-up visit.

The participant will be discharged and will sign the study completion forms and receive remuneration for participating in the study.

4.8.7 UNSCHEDULED VISITS

An unscheduled visit is defined as an interim visit requested by the participant or investigator due to an unanticipated problem. Data recorded at these visits will be entered into the database. Only relevant and applicable unscheduled visit information will be included in the final report as deemed necessary by the lead investigator.

4.9 SUMMARY OF STUDY PROCEDURES

Table 3 summarizes the visits and procedures for the study.

Table 3: Summary of visits and procedures for the study.

	V1 Screen & fit	V2 Disp Pr1	2Wk home rating Pr1	V3 1-month progress Pr1	V4 Disp Pr2	2Wk home rating Pr2	V5 1-month progress Pr2	V-Exit
Consent process	X		2	2		į.		
CL history and wear schedule	х	x		x	x		х	
Health & medication	X	Х		X	X		X	
	х							

	V1 Screen & fit	V2 Disp Pr1	2Wk home rating	V3 1-month progress	V4 Disp Pr2	2Wk home rating	V5 1-month progress	V-Exit
			Pr1	Pr1		Pr2	Pr2	e.
				2	s			
	х							
	х							
Study lens optimised fitting (both lens types)	x							
Dispense study CLs*	8	Х	6	3	X			3
	х	X		х	х		Х	
Spherical over- refraction with study CLs (if applicable)	х	х		x	х		х	
	x	х		x	x		х	
Complete subjective rating in office		X		X	X		x	
			х			X		×
				х			х	8.0
	х	x**		х	X**		x	X**
Study completion and Exit								х

^{*} Additional lenses may be dispensed at scheduled or U/S visits if there is lens defect, or lens damage.

^{**} Not required if visit concurrent with previous one.

5 MONITORING PROTOCOL ADHERENCE

Adherence to study visit windows, lens wearing schedule, and time windows around other data collection points (i.e. subjective ratings) will be monitored internally by CORE. Deviations from the windows described in the protocol will be reported in the study report. Major protocol deviations will be reported to the Sponsor and the University of Waterloo's Office of Research Ethics (ORE) within 7 days of becoming aware of them (as per ORE's guidelines).

6 POTENTIAL RISKS AND BENEFITS TO HUMAN PARTICIPANTS

This is a minimal risk study because of the use of marketed products and standard optometric assessments.

Contact lenses in this study will be worn on a daily wear basis. Complications that may occur during the wearing of contact lenses include discomfort, dryness, aching or itching eyes, excessive tearing, discharge, hyperemia and variable or blurred vision. More serious risks may include photophobia, iritis, corneal edema or eye infection. Although contact lens-related infections are very infrequent, the possibility does exist. The incidence of infection due to daywear soft lenses is 0.035%. Almost always an infection will occur only in one eye. This risk is assumed by 35-million Americans who currently wear contact lenses.

When contact lenses are worn on a daily wear basis there is a small risk of an adverse event compared to not wearing contact lenses. When contact lenses are worn on an extended wear basis, there is a significantly increased risk of an adverse reaction compared with wearing contact lenses on a daily wear basis.

Additionally, it is possible that participants may experience temporary discomfort associated with the study procedures /products/devices/eye drops (sodium fluorescein) including: burning and stinging, blurred vision, sandiness or grittiness, light sensitivity, dryness, itching, crusty eyes and foreign body sensation.

Routine clinical procedures including auto-refraction, auto-keratometry, visual acuity, anterior ocular health assessment, and contact lens fitting will be used. In addition, high magnification imaging (including video and still images) of the lens fit may be made using 35 mm or digital cameras.

There might not be direct benefits to the participants in this study. However, participation in a study may contribute to scientific research information that may be used in the development of new contact lens products. In addition, participants will receive an examination of the front part of their eyes and may have the opportunity to try a different type of soft contact lenses at no cost to them.

This study may help the study sponsor to better understand the performance of the products being used in this study.

7 ADVERSE EVENTS

7.1 ADVERSE EVENT DEFINITIONS

An 'adverse event' refers to any undesirable clinical occurrence in a participant, whether it is considered to be device-related or not. Adverse events (AE) may be classified as 'unanticipated adverse device effects,' 'serious adverse events,' 'significant adverse events,' or 'non-significant adverse events,' as defined below.

A number of conditions may result in temporary discontinuation until resolution. These include corneal infiltrates, corneal staining, limbal injection, bulbar injection or bulbar and tarsal conjunctival abnormalities.

See SOP012_v01 for a description of adverse events, including management and reporting (Appendix 26).

Classification	Definition
Serious Adverse Event	Those events that are life-threatening, or result in permanent impairment of a body function, or permanent damage to a body structure or necessitate medical (therapeutic) or surgical intervention to preclude permanent impairment of a body function or permanent damage to a body structure.
Significant Adverse Event	Those non-serious adverse events that occur with contact lens usage that are not sight-threatening but are usually symptomatic and may warrant therapeutic management and /or temporary or permanent discontinuation of contact lens wear.
Non-Significant Adverse Events	Those less severe non-serious adverse events that occur with contact lens usage that are not sight-threatening, may or may not be symptomatic and may warrant palliative management, such as ocular lubricants or temporary interruption of contact lens wear.
Unanticipated Adverse Device Effect	Adverse events in a study that were not previously identified in the protocol in terms of nature, severity, or degree of incidence. An Unanticipated Serious Adverse Device Effect is an unanticipated adverse event that is serious in nature and caused by or associated with the device and is considered reportable.

AE classification, coding (for reporting to the sponsor) and examples are provided in the following table of Contact Lens Adverse Event Classification and Reporting table:

Code	Condition	Reporting				
Serious	Serious Adverse Events					
01	Presumed infectious keratitis or infectious corneal ulcer					
02	Permanent loss of ≥ 2 lines of best spectacle corrected visual acuity (BSCVA)	- 2000 - 1000 - 1000				
03	Corneal injury that results in permanent opacification within central cornea (6mm)	For all serious AEs:				
04	Uveitis or Iritis (e.g. presence of anterior segment inflammation as described in ISO 11980, Annex B) Notify spon soon as po					
05	Endophthalmitis	within 24 hours;				
06	Hyphema	ORE reporting				
07	Hypopyon	hours as per requirements				
08	Neovascularization within the central 6mm of cornea	requirements				
00	Other serious event					
Significant Adverse Events						
11	Peripheral (outside central 6mm), non-progressive, non-infectious ulcer	Notify sponsor as				
12	Symptomatic corneal infiltrative event	soon as possible, within 5 working				
13	Superior epithelial arcuate lesions (SEALs) involving epithelial split	days; ORE				

		1 (22)2			
14	Corneal staining ≥ dense coalescent staining up to 2mm in diameter (e.g. moderate, ISO 11980 grade 3)	reporting as per requirements			
15	Corneal neovascularization ≥ 1.0mm vessel penetration (e.g. ≥ ISO 111980 Grade 2), if 2 grade change from baseline				
16	Any temporary loss of ≥ 2 lines BSCVA for ≥ 2wks				
17	Any sign and/or symptom for which participant is administered therapeutic treatment or which necessitates discontinuation of lens wear for ≥ 2 weeks				
10	Other significant event				
Non-si	Non-significant Adverse Events				
21	Conjunctivitis (bacterial, viral or allergic)				
22	Papillary conjunctivitis if ≥ mild scattered papillae/follicles approximately 1mm in diameter (e.g. ISO 11890 Grade 2), if 2 grade change from baseline	Notify sponsor as			
23	Asymptomatic corneal infiltrative events	soon as possible, within 5 working days; ORE			
24	Any sign and/or symptom for which temporary lens discontinuation for > 1 day is recommended (if not already classified)	reporting as per requirements			
20	Other sign and/or symptom warranting classification as a non-significant adverse event				

7.2 NORMAL OR ADAPTIVE SYMPTOMS

Transient symptoms such as end-of-day dryness, lens awareness, itching or burning or other discomfort may occur with contact lens wear and may occasionally reduce wearing time. These are not reported as adverse events unless in the investigator's opinion they are unexpected in nature, severe or have a high rate of occurrence.

7.3 PROCEDURES FOR ADVERSE EVENTS.

Treatment of an adverse event will depend on its nature and severity. Based on the clinical judgment of the investigator the participant may be referred to an ophthalmologist for treatment. The investigator will attempt to determine whether the reaction is related to the test device or a result of other factors. An adverse event form (Appendix 17) will be completed for each adverse event. If both eyes are involved, a separate adverse event form will be completed for each eye. Whenever possible, the adverse event will be photo-documented.

[figure not shown]
Expenses incurred for medical treatment as part of study participation will be paid by the sponsor (bills and prescription receipts kept). The participant must be followed until resolution or no further change is anticipated and/or referred for further care with the appropriate health care

professional and/or recorded as being under appropriate health care as per investigator's discretion. A written report will be completed indicating the subsequent treatment and resolution of the condition.

7.4 REPORTING ADVERSE EVENTS

All potential Serious and Unanticipated Adverse Device Effects that are related or possibly related to participant's participation will be reported to the Principal Investigator and the sponsor within 24 hours of the investigator becoming aware of the event. The Investigator will report Serious Adverse Events to the ORE within 24 hours of the investigator becoming aware of the event and as per ORE requirements (by fax, mail/delivery, phone, or email). All fatal or life threatening events will be reported immediately to the ORE.

Significant and Non-Significant Adverse Events will be reported to the sponsor as soon as possible, but no later than 5 working days after the occurrence. The Investigator will report the event to the ORE as per ORE requirements (by fax, mail/delivery, phone, or email). Sponsor contact details are:

8 DISCONTINUATION FROM THE STUDY

A participant's study participation may be discontinued at any time if, in the opinion of the sponsor or the investigator it is in the best interest of the participant. All discontinuations will be fully documented on the appropriate study forms and the Discontinuation Form will be completed. The following is a list of possible reasons for discontinuation from the study:

- Screening failure: Participants will be discontinued if they do not meet the inclusion and exclusion criteria outlined in section 4.6.2.
- Unacceptable performance with products to be used in study: Participants may be discontinued if they are unable to achieve acceptable comfort and /or vision with the study products.
- Positive slit lamp finding: Participants may be temporarily or permanently discontinued from the study depending on the severity of the condition and on the judgement of the investigator.

- Adverse event: If a participant experiences an adverse event during the study they may be discontinued based on the clinical judgement of the investigator.
- Symptoms: If the participant has persistent symptoms they may be discontinued based on the clinical judgement of the investigator.
- Disinterest, relocation or illness: The participant may choose to discontinue due to reasons within or beyond their control.
- Violation of protocol or non-compliance: The participant will be discontinued if they are unable or unwilling to follow the protocol specified visit schedules and/or study procedures.
- Instillation of topical ocular medication: The participant will be discontinued if they elect to
 use a topical ocular medication during the study unless that topical ocular medication is
 prescribed for a limited duration (less than two weeks) to treat a transient condition; in
 this case the participant may remain an active participant (at the discretion of the
 investigator) after stopping topical ocular medication following resolution of the ocular
 condition).
- Lost to follow-up: The participant will be discontinued if they cannot be contacted and do
 not return for a final exit visit, and if the investigator has made a reasonable effort to
 contact the participant for a final study visit.
- Premature termination of the study by the sponsor, CORE or the Office of Research Ethics at the University of Waterloo.

A discontinuation form (Appendix 12) will be completed, which requires the signatures of both the participant and the investigator except where the participant is lost to follow-up in which case only the signature of the investigator is required.

9 DEVICE MALFUNCTIONS

A device malfunction means the failure of the device to meet its performance specification or otherwise perform as intended. Any defective lens that is likely to cause or contribute to a Serious Adverse Event should be reported to the Principal Investigator and the sponsor within 24 hours of the investigator becoming aware of the malfunction. The ORE would also be notified within 24 hours of any device malfunction that may contribute to a Serious Adverse Event.

Other defective lenses should be reported to the Sponsor as soon as possible (usually in weekly study updates to the Sponsor).

This clinical study will also ascertain satisfaction or preference with subjective attributes such as comfort, vision, or lens handling. Responses to these subjective questionnaires will not be considered as complaints or device malfunctions.

10 STUDY COMPLETION AND REMUNERATION

At the last scheduled protocol visit a study completion form (Appendix 13) will be completed, which requires the signatures of both the participant and the investigator. The participants will also be provided with a letter of appreciation (Appendix 15).

Once their involvement in the study is complete, participants will be informed about receiving feedback following study completion in the Letter of Appreciation (Appendix15).

11 STATISTICAL ANALYSIS AND DATA MANAGEMENT

11.1 SAMPLE SIZE CALCULATION

Sample size was calculated using the mean comfort rating data from the previous pilot PIANO study (EX-MKTG-83). The data from the PIANO-2 will be pooled with data from the pilot PIANO study, therefore anyone who participated in the pilot study will be excluded from participating in the PIANO-2 study.

A total sample size of 44 is recommended to provide a minimum power of 90 with an alpha of 0.05 in a two-tailed t-test to detect a difference of 1 comfort unit (scale of 0-10). Based on the results from the pilot study (i.e. PIANO Study) the sample size needed for PIANO-2 will be aimed at 26 to complete (i.e. total of 44 minus the 18 completed participants from the pilot study). Therefore, it is recommended that at least 30 subjects are dispensed in the PIANO-2 study, with a target of 26 to complete.

11.2 STATISTICAL ANALYSIS

All data will be analyzed by CORE at the University of Waterloo. Data analysis will be conducted using Statistica, SPSS or SAS. Descriptive statistics will be provided on information regarding baseline variables (age, gender, refractive error distribution, etc.). Analysis of variables will be conducted separately on each eye, and data will not be pooled. For assessments conducted for each eye separately, the right eye will be used for analysis if there is no difference between eyes. If a general difference is found (e.g. for paired t-test / Wilcoxon matched pairs) between OD and OS, a comment will be provided.

A Binomial test will be used to analyze the results for the count data of subjective preferences. The number of "no preference" will be evenly distributed to the two options on the basis they would be equally likely to choose either.

Table 4 lists the primary study measures and anticipated statistical procedures.

Table 4: Study measures and anticipated statistical procedures

Variable	Analysis	Statistical test	
Analogue scales/Numeric scales/Preference scales/VA Lens parameters Biomicroscopy (continuous variables)	Effect of lens type	RMANOVA/MANOVA/ Friedman Wilcoxon matched pairs test Tukey HSD post hocs Paired t-test Chi-square test	
Biomicroscopy (ordinal variables)	Effect of lens type	Friedman Wilcoxon matched pairs test	
Analogue scales/Numeric scales/Lens parameters, Biomicroscopy (continuous)	Relationship between slit lamp findings and analogue scales	Pearson correlation - r	
Biomicroscopy (ordinal variables)	Relationship between slit lamp findings and analogue scales	Spearman correlation - rho	

The critical alpha level for statistical significance will be set at $p \le 0.05$, with no adjustments for multiple comparisons.

All participants who were evaluated will be used in the analysis. In the event of missing data, individual data points will be excluded in the analysis and not extrapolated from the collected data.

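### The per-eye rule in section 11.2 is inconsistent, defines no lens comparison when the eyes differ, and leaves collected left-eye data out of the supportive analyses

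*Combined protocol and SAP*

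**What the plan says.** Three consecutive sentences in section 11.2 govern measurements taken on each eye:

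1. "Analysis of variables will be conducted separately on each eye, and data will not be pooled".
2. "For assessments conducted for each eye separately, the right eye will be used for analysis if there is no difference between eyes".
3. "If a general difference is found (e.g. for paired t-test / Wilcoxon matched pairs) between OD and OS, a comment will be provided".

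Table 4 in the same section lists acuity, lens parameters and biomicroscopy among the variables tested for an effect of lens type, and plans correlations between slit-lamp findings and the analogue scales. Significance is set at p ≤ 0.05, "with no adjustments for multiple comparisons".

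Section 2 names comfort and dryness (ratings and preferences) as primary measures and handling ratings as secondary. Sections 4.8.3 to 4.8.6 describe these ratings without any split by eye. Acuity, lens parameters and biomicroscopy are in neither list, so they are supportive.

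**The concern.** Sentence 1 calls for an analysis of each eye; sentence 2 calls for the right eye alone under a condition; sentence 3 covers the other case but names no analysis. The plan does not say what counts as no difference, at which visit or with which lens this is judged, or which eye or eyes enter the lens comparison once a difference is found. Two analysts could follow section 11.2 faithfully and report different results.

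Where the right eye alone is used, the left eye's information is left out although the OD–OS check presupposes that it was collected. Similar average values in the two eyes do not make the left eye redundant. It still reduces the variance of the lens comparison, and it may carry a finding that the right eye does not. A participant-level rating correlated with right-eye findings also ignores any left-eye finding that influenced the rating.

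**Working it through.** **The plan's own figures.** The documents attach no number to the per-eye rule. The sample size in section 11.1 rests on comfort: "A total sample size of 44 is recommended to provide a minimum power of 90 with an alpha of 0.05 in a two-tailed t-test". The subtraction is correct (44 − 18 = 26 completers in this study). The SD is not stated; for a paired t-test, 44 participants and a 1-unit difference imply an SD of paired differences of 2.00. None of this involves per-eye data.

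**Precision.** Let σ² be the variance of the between-lens difference in one eye, and r the inter-eye correlation of that difference. Assume equal variance and the same lens effect in both eyes.

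- Right eye alone: variance σ².
- Mean of both eyes: σ²(1 + r)/2.
- Proportional reduction: (1 − r)/2.
- Equivalent number of participants at 26 completers: 26 ÷ [(1 + r)/2].

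The documents do not give r; the range is assumed. Power is for a two-sided paired t-test at 0.05 with 26 participants and an illustrative lens effect of 0.5 SD of the right-eye paired difference. The right eye alone gives 68.8%.

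| r (assumed) | (1 + r)/2 | Variance reduction | Equivalent participants | Power, two-eye mean |
|---|---|---|---|---|
| 0.5 | 0.75 | 25% | 34.7 | 80.8% |
| 0.7 | 0.85 | 15% | 30.6 | 75.7% |
| 0.8 | 0.90 | 10% | 28.9 | 73.3% |
| 0.9 | 0.95 | 5% | 27.4 | 71.0% |

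**Correlations with ratings.** Suppose a rating tracks the two-eye mean of a finding whose own inter-eye correlation is c. Using the right eye alone multiplies the correlation by √[(1 + c)/2]: √0.75 = 0.87 at c = 0.5 and √0.90 = 0.95 at c = 0.8 (both assumed).

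**What an OD–OS check can show.** If the check is one of the tests named as examples, at p ≤ 0.05, the paired t-test has this power:

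- 26 participants: 31.3% for an eye difference of 0.3 SD and 68.8% for 0.5 SD; 80% power needs 0.57 SD.
- 44 participants: 49.4% and 90.0% respectively.

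A non-significant result is therefore weak evidence that the eyes agree.

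**Left-only findings.** Suppose k participants have left-eye findings of equal grade and no right eye has any. The exact signed-rank p-value is 2 × 0.5^k. At k = 5 of 26 (19%), p = 0.0625, so no difference would be declared and the right-eye comparison would show nothing. With the normal approximation the largest such k is 3 (p = 0.083). If one-sided findings fall equally on both sides, a test of the average difference tends to find nothing, and the left-eye half is left out.

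**The case against.** **The three sentences can be read in sequence:** do not pool eyes, let the right eye stand for the pair when they agree, and comment when they do not. This is a fair reading and softens the conflict between the first two sentences. It still supplies no lens comparison when the eyes differ, and no criterion for agreement.

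**One eye per participant is a valid way to handle correlated eyes.** This stands. It avoids counting two eyes as independent and does not inflate type I error. A reader might infer that the lens comparisons are biased or their error rate is inflated; the documents do not support that.

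**No stated objective is touched.** This stands, and it limits the severity.

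**Safety capture is separate.** A reader might infer that left-eye problems are missed, particularly as section 6 says "Almost always an infection will occur only in one eye". That sentence concerns infection, which section 7.1 classes as a serious adverse event. Section 7.3 has adverse events documented by eye, and nothing in section 7 limits recording to the right eye. At the 0.035% incidence in section 6 (no time base given), 44 participants would yield 44 × 0.00035 ≈ 0.015 infections. The infection statement therefore adds nothing here. What can drop out is left-only grades below the section 7.1 thresholds.

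**The significance-test trigger is inferred.** Also correct. The tests appear only as examples, in the sentence about commenting, and no threshold is tied to the right-eye rule. The power and p-value figures for the OD–OS check depend on that inference; the precision figures do not.

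**Conclusion.** The point holds as a matter of clarity and efficiency in the supportive analyses. Section 11.2 gives inconsistent instructions and leaves one case without an analysis. Where the right-eye rule applies, the lens comparisons of acuity, lens parameters and biomicroscopy, and the slit-lamp/rating correlations, lose left-eye information.

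A reader might infer that half the data are lost. That is true only of the count of eye measurements (26 of 52 eyes at 26 completers). The variance reduction forgone is about 5% to 25% for r between 0.9 and 0.5. That range is assumed, as are equal variances and a common lens effect in the two eyes.

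Severity is low to moderate: comfort, dryness and handling ratings and the sample size of 44 do not change, and adverse events in either eye are still recorded.

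**What to change.** Replace all three sentences with one prespecified rule that has no OD–OS pretest. Removing only the first two would leave the third without a purpose.

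- **Continuous per-eye measures:** analyse the participant mean of OD and OS. Alternatively, use a mixed model with eye nested in participant and a participant-by-lens term, so that the two eyes' lens differences are not treated as independent.
- **Ordinal slit-lamp grades:** use a both-eye analysis that accounts for clustering by participant. Give the worse eye as a descriptive summary only, because the worse eye may not be the same eye under the two lenses.
- **Correlations with ratings:** use one both-eye value per participant, defined in advance.
- **Descriptive tables:** show OD and OS separately by lens, so that left-only findings remain visible.

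The cost is SAP wording and slightly more programming. The planned OD–OS comparison already presupposes measurements on both eyes, so no new data collection should be needed. Many procedure names in Table 3 are not legible in the public text, so confirm this against the case report forms.

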2 OBJECTIVES

The objective of the study is to evaluate the subjective acceptance of Biofinity Toric test lens when worn on a daily wear modality over 1 month.

The primary study measures are:

- Comfort subjective ratings (0-10 scale) and lens preference with respect to comfort (5step Likert)
- Dryness subjective ratings (0-10 scale) and lens preference with respect to dryness (5step Likert)

The secondary study measures are:

Handling subjective ratings (0-10 scale)

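### Splitting 'no preference' answers evenly and then applying a Binomial test to the full count weakens both primary preference tests as ties increase, and gives no usable count when the ties are odd in number

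*Combined protocol and SAP*

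**What the plan says.** Section 2 lists preference among the primary study measures, once as "lens preference with respect to comfort (5step Likert" and once as "lens preference with respect to dryness (5step Likert". Section 11.2 assigns the test: "A Binomial test will be used to analyze the results for the count data of subjective preferences". It then disposes of the ties by stating that the 'no preference' answers "will be evenly distributed to the two options on the basis they would be equally likely to choose either". It has no provision for an odd number of them.

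Table 4 in the same section also puts preference scales in a mixed row ("Analogue scales/Numeric scales/Preference scales/VA Lens parameters") beside RMANOVA/MANOVA, Friedman, Wilcoxon matched pairs, Tukey post hocs, the paired t-test and chi-square. It does not say which of these, if any, stands beside or replaces the Binomial test.

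Section 11.1 says "The data from the PIANO-2 will be pooled with data from the pilot PIANO study". The total of 44 comes from 26 new completers plus 18 from the pilot and is based on the comfort rating. No tie rate or expected preference is given anywhere.

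**The concern.** If undecided participants really were equally likely to choose either lens, t of them would contribute a random count with variance t/4. Giving exactly t/2 to each side contributes none. The Binomial test on the split count nevertheless treats all N answers as independent fair choices. Each tied pair therefore enlarges the denominator and pulls the share towards one half without carrying information, and the p-value is generally larger than the data warrant.

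When t is odd, the split produces a half-count. The analyst must then round towards or away from the leading lens, possibly after seeing the data, and that choice can put p on either side of 0.05.

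Both faults fall on two primary measures. Conservatism is not a safe direction here. The hypothesis in Section 3 is that the test lens is accepted at least as well as the control, so a non-significant preference result could be read as support for equality. A test that misses real differences would also miss a real preference for the control lens.

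**Working it through.** **Inputs.** N = 44 pooled, or 26 if PIANO-2 is analysed alone (Section 11.1). Alpha is 0.05 without multiplicity adjustment (Section 11.2). Assumed: a two-sided test (Section 11.1 uses two tails for the t-test only), tie rates of 10-40%, and 70% of stated preferences for one lens. The plan gives no power or size figure for preference, so there is none to reproduce; 44 = 26 + 18 is the only arithmetic.

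**Variance.** Let A and B be the counts preferring each lens, T the ties and τ the tie rate. The split count is A + T/2 = N/2 + (A − B)/2. Under no preference its variance is N(1 − τ)/4, while the test assumes N/4. At N = 44 the test assumes 11; the true value is 44 × 0.7/4 = 7.7 at 30% ties and 44 × 0.6/4 = 6.6 at 40%.

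**Rejection limit.** At N = 44 the split test needs 29 v 15 (p = 0.0488); 28 v 16 gives p = 0.0961.

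**Single data sets** (one lens / other lens / none):
- 23/9/12: split 29 v 15, p = 0.049; sign test on 23 of 32, p = 0.020. Both reject.
- 21/9/14: split 28 v 16, p = 0.096; sign test on 21 of 30, p = 0.043. The conclusions differ.
- 23/10/11: split 28.5 v 15.5; p = 0.096 rounded inward or 0.049 rounded outward; sign test on 23 of 33, p = 0.035.

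With an even number of ties up to 12 of 44, the two tests reject at the same counts. From 14 to 22 even ties, the split test needs one more participant on the preferred side.

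**Size and power by exact enumeration.** T ~ Binomial(44, τ), then A ~ Binomial(44 − T, p), with p = 0.5 for size and 0.7 for power. Ranges run from half-counts rounded inward to rounded outward. The last column is outward minus inward power, differenced before rounding.

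| Ties | Size, split | Size, sign | Power, split | Power, sign | Rounding alone decides |
|---|---|---|---|---|---|
| 10% | 3.1-4.6% | 3.4% | 66.1-72.1% | 67.5% | 5.9% |
| 20% | 2.2-3.4% | 3.3% | 54.8-61.8% | 61.4% | 7.0% |
| 30% | 1.4-2.4% | 3.1% | 41.6-49.2% | 53.8% | 7.6% |
| 40% | 0.8-1.4% | 3.0% | 27.6-34.9% | 46.5% | 7.3% |

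The number of ties is odd in about half of trials at these rates.

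**PIANO-2 alone (N = 26), same assumptions.** Power is 14.7-21.4% v 32.7% at 30% ties, and 7.8-12.8% v 27.3% at 40%.

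**Random allocation, as the rationale implies (N = 44).** Size returns to 4.9%, but power is only 46.3% at 30% ties and 35.7% at 40%.

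**The case against.** The strongest reply is that the harm depends on an unknown tie rate. Up to about 20% ties the sign test's power lies inside the split test's rounding range, so the change may gain nothing. The sign test beats both roundings only from about 25% (57.5% against 48.4-55.7%). This stands and limits the size of the point. It does not remove the missing rounding rule, which matters at 10% ties as well.

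The rule is also pre-specified and conservative. That is broadly true: size exceeds 5% only with outward rounding at very low tie rates (5.3% at 5% ties, 5.5% at 2%). But pre-specifying a mismatched test does not mend it.

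A third reply is that the sign test answers a different question by dropping undecided participants. The share after the split is indeed a valid estimate of P(test) + 0.5 × P(no preference). Its null value of one half, however, means P(test) = P(control), which is also the sign test's null. The fault lies in the test, not in the share.

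Fourth, the plan does not say the Binomial test is exact, and a normal approximation accepts half-counts. At N = 44, though, 28.5 gives z = 6.5/√11 = 1.9598, just short of 1.9600. The approximation therefore behaves like inward rounding and recovers no power.

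Two further limits stand. The rounding figures are for a 70:30 alternative; under no preference they are about 1.5%, 1.2%, 0.9% and 0.6% at 10-40% ties. And since the text names the Binomial test for preference counts, the Table 4 ambiguity is secondary.

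**Conclusion.** The tie rule is wrong as written and should be fixed. The test's variance does not match the count it is given, and the rule is incomplete for odd ties. At N = 44 and 70:30, the power lost against the sign test is negligible at 10% ties, about 5 to 12 percentage points at 30% (53.8 − 49.2 = 4.6; 53.8 − 41.6 = 12.2) and about 12 to 19 at 40% (46.5 − 34.9 = 11.6; 46.5 − 27.6 = 18.9). An unstated rounding choice would decide significance in roughly 6-8% of trials per measure under that alternative. The mechanism does not depend on the assumptions; the magnitudes rest on the assumed tie rate, preference split and two-sided test. The comfort-rating sample size is not affected.

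**What to change.** Replace the even-split sentence in Section 11.2 with wording such as:

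> *Preference for comfort and preference for dryness will each be tested with a two-sided exact binomial (sign) test against 50% among participants who state a preference. The number and percentage with no preference, and the share of all participants preferring each lens, will be reported alongside.*

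State that this test decides for preference, and take preference scales out of the mixed row in Table 4.

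An alternative is to name the Wilcoxon signed-rank test on the 5-step response, coded −2 to +2, as the single preference test. It uses strength of preference, but it needs an equal-step coding the plan does not state, drops zeros in its standard form, and was not evaluated in the calculations here. Random allocation of ties is less attractive: the result would hang on a random draw for little gain in power.

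The cost is one or two sentences, with no new data and no change to N. The downside is that the effective sample is only those who state a preference, so the result must be read with the 'no preference' percentage. A 6/0/38 outcome gives sign-test p = 0.031 although 38/44 = 86% have no preference.
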